- (n) The MAS will be completed where appropriate translations are available at Screening on D -42 (\pm 5 days) through D -35 (\pm 5 days). Thereafter, the MAS will be completed on Days 22-28 of each 28-day cycle through C15 and on Days 22-28 of odd-numbered cycles at C17 and beyond. The MAS must be completed at EOT and continuing for 7 days total unless an MAS was completed within the previous 14 days. The time window for starting the MAS is \pm 2 days.
- (o) Study drug bezuclastinib will be dispensed to the subject on Day 1 of each cycle for daily at-home administration. Treatment will be continuous; there will be no gaps between cycles. On days of a scheduled clinic visit, study drug will be administered at the clinic after visit procedures and assessments are performed.
- (p) A Study Drug Diary will be dispensed to the subject at the start of each cycle. Beginning at Cycle 15, subjects will be provided with diaries for use over 2 cycles. Subjects bring their diary with them to each study visit. Diary information will be reviewed and/or collected by the site during study visits.
- (q) From the signing of the ICF until the start of study treatment (C1D1), only SAEs or AEs related to on-protocol procedures will be collected. TEAEs will be collected from the start of study treatment until 30 days after the last dose of study drug. All medications will be recorded at Screening and collected through 30 days after the last dose of bezuclastinib. Any SAEs considered to have at least a possible relationship to the study drug and discovered by the Investigator at any time period after EOT should be reported.
- (r) Survival follow-up may be done via phone (with subject or referring physician).
- (s) Includes the recording of new anticancer therapy (therapy type, start and stop dates, and response to treatment).

Table 2: Schedule of Pharmacokinetics, Pharmacodynamics, and Biomarker Assessments

		Screening	Cycle 1			Cycle 2			Cycles 3-15 (a)	Odd-Numbered Cycles (C17 + beyond) (a)	EOT
Study Day		-42 to -1	1	2	15	1	2	15	1	1	
Blood sample for PGx (b)		X (b)									
Buccal swab for TPSAB1 gene (HAT) (c)		X (c)									
Blood sample for bezuclastinib PK	Predose: -30 min		X	X	X	X	X	X	X	X	
	Postdose: 1 h (± 5 min), 3 h (± 15 min), 5 h (± 15 min), 8 h (± 30 min)		X (d)			X (d)					
	Any time during Study Visit										X

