For the following endpoints, PFS and OS will be summarized using Kaplan-Meier Product-Limit survival analysis, including the estimates of 25%, 50%, and 75% percentiles and 95% confidence intervals, and DOR and TTR will be summarized with mean and standard error (if data warrant):

- DOR, defined as the time from the date of first CR, CRh, PR, or CI to the date of disease progression or death from any cause, whichever occurs first. DOR can only be determined in subjects who have CR, CRh, PR, or CI.

- TTR, defined as the time from the date of randomization/first dose of study drug until the first documented response (CR, CRh, PR, or CI). Time to best response will also be calculated.
- PFS, defined as the date of randomization/first dose of study drug to the date of first documented confirmed disease progression or death from any cause, whichever occurs first.
- OS, defined as the date of randomization/first dose of study drug to the date of death from any cause.

The following censoring rules will apply to subjects who survive at the end of the study:

- All subjects will be censored at the last date of study participation.
- Subjects who are lost to follow-up and subjects who discontinued study for any reason will be censored at the last date of contact.

An assessment of OS and PFS will be performed with and without censoring for subsequent therapy.

Changes in spleen and liver sizes will be assessed by MRI and palpation.

Evaluation of biomarkers of mutation burden and VAF in bone marrow or other samples as appropriate before and after treatment with bezuclastinib ex vivo. Potential biomarkers will be correlated with clinical outcomes.

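### Section 8.7 censors PFS at last study participation or contact instead of the last disease assessment, which biases Kaplan-Meier PFS upward

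*Protocol*

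**What the plan says.** Section 8.7 lists the definitions of DOR, TTR, PFS and OS together. On estimation it states that "PFS and OS will be summarized using Kaplan-Meier Product-Limit survival analysis", while "DOR and TTR will be summarized with mean and standard error (if data warrant".

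Directly below the four definitions comes a single block of rules: "The following censoring rules will apply to subjects who survive at the end of the study". There are two of them: "All subjects will be censored at the last date of study participation", and "Subjects who are lost to follow-up and subjects who discontinued study for any reason will be censored at the last date of contact". No endpoint is named, and nothing elsewhere in the protocol ties PFS or DOR censoring to a disease assessment. Section 8.7 adds that OS and PFS will each be assessed with and without censoring for subsequent therapy. DOR is not included in that.

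On follow-up, Table 3 schedules marrow, imaging and overall response assessment up to the end-of-treatment visit and no further. Section 6.15.6 then keeps subjects in survival follow-up for at least 2 years, with contacts every 3 months (Table 1). Footnote (r) to Table 1 says "Survival follow-up may be done via phone (with subject or referring physician". Footnote (s) explains the disease status item: "Includes the recording of new anticancer therapy (therapy type, start and stop dates, and response to treatment".

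**The concern.** Death can be established by a phone call, so last contact is a sound censoring date for OS. Progression under the modified IWG-MRT-ECNM criteria has to be found by marrow, imaging and laboratory review, and none of these is scheduled after end of treatment. Section 4.3.1 lets subjects stop drug without progression, for example for an adverse event, an interruption of more than 28 days, transplantation or an Investigator decision. Under the stated rule, someone who stops for toxicity at month 6 and is last phoned at month 30 is counted as progression-free for 30 months, of which 24 are unassessed.

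Part 2 Stage 2 has no control arm, so its PFS will be read as an absolute figure with no concurrent arm sharing the error. PFS is also summarized by dose cohort, and a cohort with more toxicity discontinuations would gain more unassessed progression-free time.

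**Working it through.** **Is there a figure to reproduce?** Not for PFS or DOR: the protocol gives no event count, precision or power for either. The only powered figure is ORR in Section 8.2 (55 subjects, 28% against 60%, one-sided alpha 0.025). The one-sample normal approximation gives power 99.9%; the exact rule (at least 23 of 55) gives 99.8%. Both satisfy the stated minimum of 90%, and neither involves the censoring rule.

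**Mechanism.** The Kaplan-Meier estimate is S(t) = product of (1 − d/n) over event times. Under the stated rule, subjects off drug stay in n, but their progressions cannot enter d. The ratio d/n is then too small and S(t) too large. Deaths still enter d, which dampens the bias without removing it. For subjects still on drug after Cycle 12, assessments are 6 cycles apart, so the rule can also add up to 6 × 28 days = 24 weeks beyond the last assessment.

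**Inputs from the protocol.** Assessments at C3, C6, C9 and C12, then every 6 cycles; 24 months of survival-only contact after stopping (the protocol's minimum).

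**Assumptions not in the protocol.** Exponential time to progression with median 18 or 30 months; median time to death 60 months, with the death hazard tripled after progression; 10, 20 or 30% per year stopping without progression, hazard −ln(1 − rate)/12 per month; accrual over 24 months; data cutoff at 60 months. For context only, Section 1.3 cites discontinuation for adverse events of 21% with midostaurin and 10% with avapritinib.

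**Results** (200,000 simulated subjects per scenario, Kaplan-Meier PFS at 24 months):

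| Progression median | Stopping per year | Stated rule | Last assessment | Assessments continued | Stated rule minus continued |
|---|---|---|---|---|---|
| 18 months | 10% | 36.3% | 33.0% | 33.2% | +3.1 |
| 18 months | 20% | 39.5% | 33.2% | 33.6% | +5.9 |
| 18 months | 30% | 42.1% | 32.7% | 33.4% | +8.7 |
| 30 months | 10% | 48.7% | 46.2% | 46.4% | +2.3 |
| 30 months | 20% | 50.7% | 45.8% | 46.4% | +4.3 |
| 30 months | 30% | 52.7% | 45.4% | 46.3% | +6.4 |

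Median PFS is overstated by 0 months (15.6 against 15.6, first row) to 5.5 months (26.7 against 21.2, last row).

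Two limits apply. First, this model gives no credit for the end-of-treatment assessment. With it added, the gap is about 2 to 7 points, and last-assessment censoring is within about 2 points of the target. Second, the last-assessment column also censors subjects who die after assessments have stopped. If those deaths count as events while survivors are censored at their last assessment, 24-month PFS falls below the target by 0.7 points (33.2 − 32.5) to 5.0 points (46.3 − 41.3).

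**DOR.** No Kaplan-Meier curve is planned. If only completed durations are averaged, phone-contact time never enters. If censored times are averaged in, the same process used as an analogue gives a mean of 19.8 to 20.3 months under last contact, against an underlying mean of 1/(ln2/18 + ln2/60) = 20.0. With the 30-month median it gives 23.9 to 24.3, against 1/(ln2/30 + ln2/60) = 28.9. Both underlying means are before visit-detection delay. Averaging cut-off times shortens the mean, which offsets or outweighs the unassessed time.

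**The case against.** The strongest defence is that PFS is secondary, untested and unpowered, and that Section 8.7 already plans a version censored at subsequent therapy. Both points are true. The first lowers the priority. The second is only partial protection: it does nothing for subjects who stop and start no new therapy, and the other planned PFS version keeps the full bias.

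Follow-up is also less bare than it might appear. Section 6.15.6 mentions disease status, footnote (s) may not be exhaustive, a response assessment is scheduled at end of treatment, and enrollment in another therapeutic study ends contact. These shorten or soften the unassessed period, but they do not create a scheduled response assessment after end of treatment.

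One could leave the matter to the SAP. But the protocol does not leave it open: it states a rule that an appropriate SAP would have to contradict.

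Two stronger readings are tempting. A reader might infer that DOR is overstated as well. The documents do not support that, because DOR is to be summarized by mean and standard error and the direction of bias depends on how censored durations enter the mean. A reader might also take the opening of the rules to mean that a subject who progressed but is alive at study end is censored. Section 8.7 makes confirmed progression a PFS event, and censoring ordinarily applies to subjects without an event. This is loose wording worth tightening, not a second defect.

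**Conclusion.** The PFS censoring rule is wrong as written. The direction is upward whenever subjects stop drug without progression and would later have progressed unseen. The size, about 2 to 9 points at 24 months (about 2 to 7 when the end-of-treatment assessment is modelled), rests on assumed progression, death and stopping rates that the protocol does not give and should be read as a range. The rule is also unsuitable for DOR, and a mean does not handle censored durations, but an overstated DOR is not established. Nor should anyone infer that the efficacy test is compromised: ORR does not use these rules. The point should be fixed, at secondary-endpoint priority.

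**What to change.** In Section 8.7, and in the SAP to match:

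- Keep last-contact censoring for OS only.
- For PFS, count documented progression or death as events whether or not the subject is alive at study end. For DOR, also count loss of response, as the Section 2 definition does and the Section 8.7 definition does not.
- Censor event-free subjects at the last adequate modified IWG-MRT-ECNM assessment. With no post-baseline assessment, censor PFS at its own time origin (randomization in Part 1 and Part 2 Stage 1, first dose in Part 2 Stage 2). Where no assessment follows the first response, censor DOR at the date of that response.
- State how deaths occurring after assessments have stopped are handled, and show the alternative as a sensitivity analysis, since that choice moved the estimate by several points in the check above.
- Summarize DOR by Kaplan-Meier.

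The cost is a few lines of text and no new data, because assessment dates are already collected. The downside is that reported PFS may be shorter.

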8.8. QUALITY OF LIFE ANALYSES

The PGIC and change and percent change from baseline in the patient-reported outcomes and quality of life scales PGIS, MC-QoL, and MAS ([Appendix I](#)) will be summarized by study part and stage (Part 1, Part 2 Stage 1, or Part 2 Stage 2) and dose cohort. These endpoints will be listed as well.

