(a) After 15 cycles, dispensation of study drug for at-home administration and study drug diary will be adjusted accordingly.

(b) At C15 and beyond, and at most other study visits, clinical chemistry, hematology, pregnancy testing (women of childbearing potential only), AE monitoring, and collection of concomitant medications will be performed.

(c) EOT assessments should be performed within 7 days of decision to permanently discontinue study treatment.

(d) Subjects should be dosed as soon as possible after randomization and preferably within 7 days before receiving their first dose on C1D1.

(e) A complete PE will be performed at Screening only. At all other study visits, a targeted PE will be performed based on Investigator’s judgment and careful evaluation of the subject’s signs and symptoms.

- (f) Height at Screening only.
- (g) A single 12-lead ECG will be performed after the subject has been resting in supine or semi-supine position for at least 5 minutes. At all predose and postdose intervals, each ECG should occur just prior to each PK blood sample collection.
- (h) On C1D1 and C2D1, a single ECG will be performed predose (within 30 min prior to dosing) and at 1 (\pm 5 minutes), 3 (\pm 15 minutes), 5 (\pm 15 minutes), and 8 (\pm 30 minutes) hours postdose.
- (i) Safety laboratory tests (hematology, chemistry) may be completed 1 day prior to the visit on C1D1 (after randomization) or on C2D1.
- (j) Serum tryptase will be collected as indicated and at all response time points. Serum tryptase will be tested locally. A blood sample will also be collected and tested at a central laboratory. Additional exploratory analyses may be performed on blood samples to further explore pharmacodynamic markers in subjects with AdvSM.
- (k) Subjects with a positive HCV antibody may be eligible if HCV RNA is undetectable on a quantitative HCV RNA assay, following discussion with the Medical Monitor.
- (l) Women of childbearing potential only. A serum pregnancy test (β -human chorionic gonadotropin) will be performed at Screening, and a urine pregnancy test will be performed at subsequent visits.
- (m) QOL assessments to include Patient Global Impression of Severity (PGIS), Patient Global Impression of Change (PGIC), and the Mastocytosis Quality of Life Questionnaire (MC-QoL). PGIC will be performed starting on C2D1.

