		of first documented disease progression, or death from any cause, whichever occurs first
		Overall survival (OS), defined as the date of randomization/first dose of study drug to the date of death from any cause
		Pure Pathologic Response (PPR), including complete remission, complete remission with partial hematologic recovery, molecular complete remission, and partial remission (Gotlib et al, 2020)
		Changes in spleen and liver size assessed by magnetic resonance imaging (MRI)
	To determine the effects of bezuclastinib on serum tryptase	Changes in the levels of serum tryptase
	To determine the effects of bezuclastinib on KIT D816V mutation allele burden	Changes in the levels of KIT D816V mutation allele burden in blood and bone marrow
	To evaluate histopathologic response in the blood and bone marrow	Change in pathologic findings in the blood and bone marrow, including mast cell infiltration, monocytosis, and eosinophilia
	To assess the PK of bezuclastinib in subjects with AdvSM	Plasma concentrations and PK parameters (eg, area under the plasma concentration-time curve [AUC] and maximum observed plasma concentration [C _{max}]) of bezuclastinib
	To assess patient-reported outcomes in subjects with AdvSM	Patient Global Impression of Change (PGIC) scale and change and percent change from baseline in the following patient-reported outcome measures: Patient Global Impression of Severity (PGIS) scale, Mastocytosis Quality of Life Questionnaire (MC-QoL), and Mastocytosis Activity Score (MAS) where appropriate translations are available (Siebenhaar et al, 2018; Siebenhaar et al, 2016)
	To explore the effect of bezuclastinib in subjects with AdvSM who are non-evaluable based on the modified IWG-MRT-ECNM response criteria	
 • Incidence of AEs, SAEs, AEs leading to dose modifications, and changes from baseline in laboratory results • PPR, including complete remission, complete remission with partial hematologic recovery, molecular complete remission, and partial remission (Gotlib et al, 2020)

Objectives and Endpoints:		
	Objectives	Endpoints
Exploratory	To explore various pharmacodynamic markers and their relationship with clinical safety and efficacy	Blood and bone marrow obtained at various timepoints throughout the trial to determine the effects of bezuclastinib on pharmacodynamic markers, including KIT D816V mutation allele burden and myeloid mutation profile as a measure of pharmacodynamic activity

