APPENDIX I. QUALITY OF LIFE ASSESSMENT TOOLS

AI-1. PATIENT GLOBAL IMPRESSION OF SEVERITY SCALE

Patient Global Impression of Severity in Symptoms Overall due to Advanced Systemic Mastocytosis (PGIS – Overall Symptoms)

Please choose the response below that best describes the severity of your symptoms overall due to your mastocytosis over the past week.

- None
- Mild
- Moderate
- Severe
- Very severe

Patient Global Impression of Severity of Gastrointestinal Symptoms due to Advanced Systemic Mastocytosis (PGIS – GI Symptoms)

Please choose the response below that best describes the severity of your gastrointestinal symptoms (e.g. abdominal pain, diarrhea, nausea, vomiting) due to your mastocytosis over the past week.

- None
- Mild
- Moderate
- Severe
- Very severe

Patient Global Impression of Severity of Skin Symptoms due to Advanced Systemic Mastocytosis (PGIS – Skin Symptoms)

Please choose the response below that best describes the severity of your skin symptoms (e.g. spots, itching, flushing) due to your mastocytosis over the past week.

- None
- Mild
- Moderate
- Severe
- Very severe

AI-2. PATIENT GLOBAL IMPRESSION OF CHANGE SCALE

Patient Global Impression of Change in Symptoms Overall due to Advanced Systemic Mastocytosis (PGIC – Overall Symptoms)

Please choose the response below that best describes the overall change in your symptoms overall due to your mastocytosis, since you started taking the study medication.

- Very much better
- Much better
- A little better
- No change
- A little worse
- Much worse
- Very much worse

Patient Global Impression of Change in Gastrointestinal Symptoms due to Advanced Systemic Mastocytosis (PGIC – GI Symptoms)

Please choose the response below that best describes the overall change in your gastrointestinal symptoms (e.g. abdominal pain, diarrhea, nausea, vomiting) due to your mastocytosis, since you started taking the study medication.

- Very much better
- Much better
- A little better
- No change
- A little worse
- Much worse
- Very much worse

Patient Global Impression of Change in Skin Symptoms due to Advanced Systemic Mastocytosis (PGIC – Skin Symptoms)

Please choose the response below that best describes the overall change in your skin symptoms (eg, spots, itching, flushing) due to your mastocytosis, since you started taking the study medication.

- Very much better
- Much better
- A little better
- No change
- A little worse
- Much worse
- Very much worse

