	mild								
	moderate								
	severe								
	very severe								
									(0-28)
Difficulty concentrating	not at all								
	mild								
	moderate								
	severe								
	very severe								
									(0-28)
Total MAS (0-252)									

**APPENDIX J. EASTERN COOPERATIVE ONCOLOGY GROUP
PERFORMANCE STATUS**

GRADE	ECOG PERFORMANCE STATUS
0	Fully active, able to carry on all pre-disease performance without restriction
1	Restricted in physically strenuous activity but ambulatory and able to carry out work of a light or sedentary nature, eg, light housework, office work
2	Ambulatory and capable of all selfcare but unable to carry out any work activities; up and about more than 50% of waking hours

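### Percent change from baseline is specified for PGIS, a set of five-category verbal items, so the reported percentage depends on an arbitrary choice of numeric codes

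*Protocol*

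**What the plan says.** Section 8.8 groups three instruments under one pair of summaries: "change and percent change from baseline in the patient-reported outcomes and quality of life scales PGIS, MC-QoL, and MAS". These are to be presented by study part, stage and dose cohort, and also listed. The secondary endpoint in Section 2, repeated in the Synopsis, has the same content: "change and percent change from baseline in the following patient-reported outcome measures: Patient Global Impression of Severity (PGIS) scale", followed by MC-QoL and MAS. The metric therefore stands in three places and is not a slip in one of them.

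PGIC is kept outside this wording, which is right. It has no baseline, since a footnote to Table 1 states that "PGIC will be performed starting on C2D1".

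Appendix I (AI-1) prints the PGIS. The first item reads "Please choose the response below that best describes the severity of your symptoms overall due to your mastocytosis over the past week". Two further items ask about gastrointestinal and skin symptoms. All three offer the same options: None, Mild, Moderate, Severe, Very severe. The form shows no numeric codes and defines no PGIS total. The MAS form (AI-4) differs in this respect: it prints a range of 0 to 28 per symptom and 0 to 252 in total.

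**The concern.** Percent change divides by the baseline value, so it has meaning only where zero and the distance from zero have meaning. PGIS gives an order of five words. Any set of equally spaced numbers in that order represents the answers equally well, yet each starting number gives a different percentage for the same answers.

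Two things follow. The reported mean percent change reflects the coding as well as the patients. And if the lowest category is coded 0, a subject who starts there has no percent change at all, even if symptoms later appear. A baseline answer of None is plausible, most obviously on the skin item: Appendix B notes that skin lesions are usually absent in aggressive systemic mastocytosis and mast cell leukemia, and Sections 4.1 and 4.2 set no minimum symptom severity. The protocol gives no expected share of such subjects. With about 7 subjects per Part 1 cohort (Section 1.3.3) and about 10 per Part 2 Stage 1 group (Section 8.2), even one or two would be noticeable in that summary.

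**Working it through.** **Inputs.** The five categories come from Appendix I (AI-1), and the metric comes from Section 8.8. The protocol gives no codes, so two common sets are assumed: 0 to 4 and 1 to 5. The plan states no figure on this point, so there is none to reproduce.

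**Formula.** Number the categories 0 to 4 in order, let b and f be the baseline and follow-up categories, and let c be the code given to None. Then

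percent change = 100 × (f − b) / (b + c).

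The numerator does not involve c; the denominator does. So absolute change in categories is free of the origin, and percent change is not.

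**Single transitions.**

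| Baseline to follow-up | Change in categories | Codes 0 to 4 | Codes 1 to 5 |
|---|---|---|---|
| Severe to Moderate | -1 | (2−3)/3 = -33.3% | (3−4)/4 = -25% |
| Moderate to Mild | -1 | (1−2)/2 = -50% | (2−3)/3 = -33.3% |
| Mild to None | -1 | (0−1)/1 = -100% | (1−2)/2 = -50% |
| Severe to None | -3 | (0−3)/3 = -100% | (1−4)/4 = -75% |
| Very severe to Moderate | -2 | (2−4)/4 = -50% | (3−5)/5 = -40% |
| Mild to Moderate | +1 | (2−1)/1 = +100% | (3−2)/2 = +50% |
| None to Mild | +1 | (1−0)/0, undefined | (2−1)/1 = +100% |

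Under codes 0 to 4, every move to None is -100%, whether it starts at Mild or at Very severe.

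**Groups (constructed examples).** The order of two groups can reverse with the coding alone.

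- Group 1, all moving from Very severe to Moderate: mean -50% (codes 0 to 4) or -40% (codes 1 to 5).
- Group 2, 60% moving from Mild to None and 40% staying at Very severe: 0.6 × (−100) = -60%, or 0.6 × (−50) = -30%.

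Group 2 looks better under the first coding and Group 1 under the second.

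The mean can also point the wrong way. If half move from Mild to Moderate and half from Severe to Moderate, the mean change is (+1 − 1)/2 = 0 categories. The mean percent change is (100 − 33.3)/2 = +33.3% under codes 0 to 4, or (50 − 25)/2 = +12.5% under codes 1 to 5.

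**After the fix.** Category counts, a shift table and change in number of categories are identical under both codings, and all are defined for a subject starting at None. No sample size or power figure changes.

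**The case against.** The strongest reply is that codes and a rule for zero baselines are ordinary content of a statistical analysis plan, and Section 8.1 leaves such handling to one that is not shown. That is fair as to missing detail: the absence of codes from the protocol is not a fault in itself. It does not answer the main point, because the protocol itself names the metric. A later document can choose an origin, but any origin is arbitrary and the percentage inherits it.

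Second, a reader might infer that subjects starting at None drop out of the PGIS analysis, or that percent change is undefined for them in every case. The documents support neither. The value is undefined only if None is coded 0; under codes 1 to 5 it can be computed, though only because of the offset. Section 8.8 also plans absolute change and listings, so these subjects remain in both.

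Third, the same objection could be pressed against MC-QoL and MAS, which are also built from verbal ratings. This partly stands. MAS has a printed scoring, and a zero total needs the lowest answer on all nine symptoms on all seven days, but its range does start at 0. The MC-QoL form in AI-3 prints no codes, so its percent change rests on scoring defined elsewhere. Both should be tied to their defined scoring, with zero baselines counted.

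Finally, it might be read as a threat to dose selection or to the primary result. Nothing in the protocol supports that. The only planned test in Section 8.7 is ORR against 0.28, and the dose-selection criteria named in Section 8.2 are safety, biomarker, clinical efficacy and PK endpoints, without patient-reported outcomes.

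**Conclusion.** The point holds as a minor one. The protocol fixes, in three places, a ratio summary for three ordinal verbal items, and the number it yields depends on the coding. A one-category improvement at the lower end of the scale doubles in size between two ordinary codings (-50% against -100%); at Severe to Moderate the difference is about 8 percentage points. The size rests on the two assumed codings and, for the zero-baseline part, on None being coded 0. The number of subjects affected cannot be estimated from the protocol. The endpoint is secondary and descriptive, absolute change and listings remain, and the primary ORR analysis, its power and its alpha are unaffected.

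**What to change.** In the Synopsis endpoint table, Section 2 and Section 8.8, remove percent change for PGIS. Summarize each of the three items by category counts at each visit and a shift table from baseline. Optionally add the proportion improving by at least one category, with a 95% confidence interval, among subjects whose baseline answer is not None, since subjects at None cannot improve; state that denominator. The one-category threshold is a suggestion and not something the protocol establishes.

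Keep percent change only for the summed MC-QoL and MAS scores under their defined scoring, and report how many subjects have a zero baseline and so no percent change.

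The cost is a wording change in three places. It needs no new data, no added visits and no change to the sample size.
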